- g Assessments involving interviews and scales must be done before the infusions. All efficacy and pharmacoeconomic assessments are PROs. PROs which are scheduled in alignment with a clinic visit can be completed in the clinic or in the remote setting within 3 days prior to the scheduled clinic visit date. Additionally, PGIC (at Week 4 only), HIT-6, EQ-5D-5L, HCRU, WPAI which are scheduled in alignment with a phone contact must be completed in the remote setting and can be completed on the day or within 3 days prior to the scheduled phone contact date.
- h The eDiary assessments will be completed in the remote setting on a daily basis.
- i At the Screening Visit, the patient must be assisted with the provisioning and training of the eDiary and training of efficacy and pharmacoeconomic assessments (PROs). Details will be provided in a separate user manual.
- j The eDiary closeout will take place at the Completion/Withdrawal Visit, while the patient is at site. Details will be provided in a separate user manual.

- k The patients will be contacted via phone every 4 weeks between infusion visits for eDiary compliance check, to ensure that selected assessments have been completed and for collection of relevant information such as AEs and concomitant medication.
- 1 PGIC at Week 4 must be completed in the remote setting.
- m At infusion visits, infusion related reactions (IRRs) must be checked as part of the overall AE collection, after infusion and before the patient is discharged from the site.
- n At infusion visits, physical examination, ECG, blood sampling (for clinical safety laboratory tests, ADA and biobank) and urine samples (for clinical safety laboratory tests and pregnancy) must be conducted before infusion. AEs, vital signs including body temperature should be checked before and after infusion.
- o The C-SSRS will be administered by the authorized rater at the clinic and prior to infusion.
- p Patients who test positive for ADA at the Completion Visit will be asked to provide up to two additional blood samples for immunogenicity testing at 12-week intervals for up to 24 weeks.
- q At infusion visits, patients must be monitored for a period of 1 hour from the end-of-infusion. Patients will be requested to stay longer should the investigator determine this is clinically warranted.
- r An unblinded pharmacist or designee is responsible for receiving, storing and preparing IMP. The pharmacist or designee will not be responsible for other aspects of the clinical trial where blinding is necessary.
- s A designated unblinded CRA is responsible for the IMP accountability.
- t Pregnancy test at Screening to be performed using serum β -HCG. At all other visits, urine pregnancy testing will be performed and in case of a positive finding, confirmatory testing will be performed via serum β -HCG.
- u Exit Interview subset: Patients undergoing the exit interviews must provide signed subset-specific Informed Consent. The exit interview will be conducted shortly (no later than 2 weeks) after the last assessment of the Week 24 Visit or Withdrawal Visit for patients who withdraw prior to Week 24. The exit interview must be conducted after all visit assessments are completed. Details will be provided in a separate exit interview guide.
- v Patients who withdraw, except for those who withdraw their consent, will be asked to attend a Withdrawal Visit 12 weeks after the last dose of IMP and undergo Safety Follow-Up evaluations. Patients who withdraw prior to Week 24 will undergo additional Efficacy Follow-Up evaluations.
- w Exploratory gene expression profiling (RNA) and metabolomics/proteomics are an integrated part of the study and are covered by the main Informed Consent.
- x Sampling for pharmacogenetics is optional and a separate signed Informed Consent must be in place to cover this analysis.
- y Whole blood samples for serum separation and potential future ADA analyses will be drawn at Week 24 and at the Completion or Withdrawal Visit.

Table of Contents

List	of Pan	els	22
List	of Abb	previations and Definitions of Terms	23
Mai	or Cha	nges Since Last Edition	26
1		luction	
	1.1	Background	30
		1.1.1 Overview	30

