	 Change from baseline in the number of monthly migraine days with use of acute medication (Weeks 1- 12)
	 Change from baseline in number of monthly migraine days with use of acute medication (Weeks 13-24)
	 Patient Global Impression of Change (PGIC) score at Week 12
	– PGIC score at Week 24

Objectives and Endpoints (continued) Objectives	Endpoints
	 Change from baseline in the number of monthly migraine days in patients with Medication Overuse Headache (MOH) (Weeks 1-12)
	 Patients with a migraine on the day after first dosing Change from baseline to Week 12 in Most Bothersome Symptom (MBS) score
	 Exploratory endpoints: Change from baseline in monthly number of Migraine attacks for each 12-week period
	 Change from baseline in monthly number of Headache episodes for each 12-week period
Secondary ObjectivesTo evaluate the health-related quality of life and work productivity impact of eptinezumab	 Key secondary endpoints: Change from baseline to Week 12 in the Headache Impact Test (HIT-6) score
	 Secondary endpoints: Change from baseline to Week 24 in the HIT-6 score
	 Change from baseline to Week 12 in the Migraine-Specific Quality of Life (MSQ v2.1) sub-scores (Role Function- Restrictive, Role Function-Preventive, Emotional Function)
	 Change from baseline to Week 12 in the Health-Related Quality of Life (EQ-5D-5L) Visual Analogue Scale (VAS) score
	 Change from baseline to Week 12 in Health Care Resources Utilization (HCRU)
	 Change from baseline to Week 24 in the MSQ v2.1 sub- scores
	 Change from baseline to Week 24 in the EQ-5D-5L VAS score
	- Change from baseline to Week 24 in HCRU
	 Change from baseline to Week 12 in the Work Productivity and Activity Impairment Questionnaire (WPAI) sub-scores (Absenteeism, Presenteeism, Work productivity loss, Activity impairment)
	- Change from baseline to Week 24 in WPAI sub-scores
• To evaluate the effect of long-term treatment	
with eptinezumab	 Change from baseline in the number of monthly migraine days (Weeks 25-36, 37-48, 49-60, 61-72)
	 Response: patients with 50% reduction from baseline in monthly migraine days (Weeks 25-36, 37-48, 49-60, 61-72)
	 Response: patients with 75% reduction from baseline in monthly migraine days (Weeks 25-36, 37-48, 49-60, 61-72)

Objectives and Endpoints (continued) Objectives	Endpoints
	 Change from baseline in the HIT-6 score (at Weeks 36, 48, 60, and 72)
	• Exploratory endpoints:

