8.5 IMP Visits (Visits 2, 5, 8, 11, 14, 17)

At the IMP Visits, the infusion is preceded by assessments of vital signs including body temperature, concomitant medications, AEs, physical examination, ECG, blood and urine sampling and C-SSRS administration.

Assessments involving interviews and scales must be administered before the infusion. PROs will be completed in the clinic the following order; HIT-6, PGIC, MBS, MSQ v2.1, EQ-5D-5L, HCRU, WPAI. Alternatively, PROs which are scheduled in alignment with an IMP visit can be completed in the remote setting within 3 days prior to the scheduled clinic visit date.

Patients must complete the daily eDiary entries prior to infusion. A compliance check of the eDiary will be conducted and the patient must be assisted with re-training if necessary. See section 9.2.2 for further details on eDiary.

Patients will be monitored for at least 1 hour following end-of-infusion and before being discharged from the clinic. Patients will be requested to stay longer should the investigator determine this is clinically warranted. After the infusion, the patients will be under observation, but not confined to bed, unless the investigator decides, based on the patient's condition, that it is in the best interest of the patient to be confined to bed. Vital signs including body temperature, infusion related reactions (IRRs) and AEs will be checked after infusion and before the patient is discharged from the site. AEs should be collected prior to assessment of IRRs.

Exit Interview subset: The exit interview will be conducted at Visit 8 (Week 24 Visit or at the Withdrawal Visit for patients who withdraw prior to Week 24). The exit interview must be conducted after all visit assessments are completed. A visit window of 2 weeks is allowed for the exit interview from the last assessment conducted for Visit 8/Withdrawal Visit (for patients who withdraw prior to Week 24). See section 9.5.1 for further details on the exit interview.

8.6 Phone Contacts (Visits 3, 4, 6, 7, 9, 10, 12, 13, 15, 16, 18, 19)

The patient will be contacted via phone every 4 weeks between infusion visits for eDiary compliance check, to ensure that selected assessments have been completed and for collection of relevant information such as AEs and concomitant medication.

A compliance check of the eDiary will be conducted and the patient must be assisted with retraining if necessary. See section 9.2.2 for further details on eDiary.

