eptinezumab	 Secondary endpoints: Change from baseline to Week 24 in the HIT-6 score Change from baseline to Week 12 in the Migraine-Specific Quality of Life (MSQ v2.1) sub-scores (Role Function-Restrictive, Role Function-Preventive, Emotional Function) Change from baseline to Week 12 in the Health-Related Quality of Life (EQ-5D-5L) Visual Analogue Scale (VAS) score Health Care Resources Utilization (HCRU) at Week 12 Change from baseline to Week 24 in the MSQ v2.1 sub-scores Change from baseline to Week 24 in the EQ-5D-5L VAS score HCRU at Week 24 Change from baseline to Week 12 in the Work Productivity and Activity Impairment questionnaire (WPAI) sub-scores (Absenteeism, Presenteeism, Work productivity loss, Activity impairment) Change from baseline to Week 24 in the WPAI sub-scores Response: Patients with a 5-point reduction from baseline to Week 24 in HIT-6 score
• To evaluate the effect of long- term treatment with eptinezumab	 Secondary endpoints: Change from baseline in the number of monthly migraine days (Weeks 25-36, 37-48, 49-60, 61-72) Response: patients with 50% reduction from baseline in monthly migraine days (Weeks 25-36, 37-48, 49-60, 61-72) Response: patients with 75% reduction from baseline in monthly migraine days (Weeks 25-36, 37-48, 49-60, 61-72) Change from baseline in the HIT-6 score (at Weeks 36, 48, 60, and 72)
	 Exploratory endpoints: Response: patients with 100% reduction from baseline in monthly migraine days Response: patients with 50% reduction from baseline in monthly headache days Response: patients with 75% reduction from baseline in monthly headache days Response: patients with 100% reduction from baseline in monthly headache days Response: patients with 100% reduction from baseline in monthly headache days Response: patients with 100% reduction from baseline in monthly headache days Change from baseline in percentage of migraines/headaches with severe pain intensity

Objectives	Endpoints

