- Response: Patients with 75% reduction from baseline in MMDs (Weeks 13-24)
- Response: Patients with 50% reduction from baseline in MHDs (Weeks 1-12)
- Response: Patients with 75% reduction from baseline in MHDs (Weeks 1-12)
- Response: Patients with a 5-point reduction from baseline to Week 12 and from baseline to Week 24 in HIT-6

For the HIT-6 response endpoints, LOCF will be used to impute a potentially missing value at Week 12 or Week 24. Baseline values will not be carried forward.

The following endpoints:

- Response: Patients with 100% reduction from baseline in MMDs (Weeks 1-12)
- Response: Patients with 100% reduction from baseline in MHDs (Weeks 1-12)
- Patients with a migraine on the day after first dosing

Will be derived according to the descriptions in Section 19.1.1.2 and 19.1.1.3 and analysed using an extended Cochran-Mantel-Haenszel (CMH) test, adjusting for one of the stratification factors (MHDs at baseline: $\leq 14 /> 14$). The rates for each dose of eptinezumab and placebo will be presented. The SAS[®] code for performing the extended CMH test is shown in Appendix IV.

Descriptive tables displaying the distribution of answers to the items in HCRU at each visit will be provided by treatment group.

Tables displaying the counts and percentage of answers to each category of response options for each item of EQ-5D-5L will be presented by visit and treatment group. Furthermore, shift tables displaying for each item in EQ-5D-5L the number and percentage of patients who decreased, increased or had no change from baseline in the item score will be provided by visit and treatment group.

For inclusion into the *addendum CSR*, the endpoints listed below will be derived according to the descriptions given in Section 19.1 and the absolute values will be analysed using an MMRM similar to the one described for the primary endpoint (see Section 12.3.2) but using treatment sequence group instead of treatment group.

No treatment comparisons will be performed for any of the efficacy endpoints after Week 24. Instead, the estimated mean values will be reported with two-sided 95% confidence intervals by treatment sequence for:

- Number of MMDs (at Weeks 1-4, Weeks 5-8, Weeks 9-12, Weeks 13-16, Weeks 17-20, Weeks 21-24, Weeks 25-36, 37-48, 49-60, and 61-72)
- HIT-6 score (at week 4, 8, 12, 16, 20, 24, 36, 48, 60, and 72)

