19.1.7 Health Care Resource Utilization (HCRU)

Migraine-specific healthcare resource utilization information will be collected in terms of outpatient health care professional visits (number of visits to doctor/genral practitioner and number of visits to a specialist), number of emergency room visits, number of hospital admissions, as well as number of overnight hospital stays during the past 4 weeks.

The items from the questionnaire will be analyzed separately.

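### Health care resource use (HCRU), a listed secondary endpoint, is tabulated visit by visit only: reports collected every 4 weeks are never summed per patient, and no between-arm estimate is given

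*Protocol*

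**What the plan says.** **Endpoint.** Under the objective on quality of life and work productivity, the protocol lists "Change from baseline to Week 12 in Health Care Resources Utilization (HCRU") and the same change to Week 24 (Synopsis; Section 2, Panel 3). SAP Section 1, Panel 1 has instead "Health Care Resources Utilization (HCRU) at Week 12" and "HCRU at Week 24". SAP Section 18 gives the reason: response frequencies will be summarised, not changes from baseline.

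**Recall.** SAP 19.1.7 lists five items: visits to a doctor or general practitioner, visits to a specialist, emergency room visits, hospital admissions, "as well as number of overnight hospital stays during the past 4 weeks". Items are analysed one by one. No count over a longer interval is derived.

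**Schedule.** Protocol Panel 2 has HCRU at baseline and at every later visit or contact. Section 8.6 states: "The patient will be contacted via phone every 4 weeks between infusion visits". Footnote g to Panel 2 adds that "HIT-6, EQ-5D-5L, HCRU, WPAI which are scheduled in alignment with a phone contact must be completed in the remote setting". Up to Week 24 this means phone contacts at Weeks 4, 8, 16 and 20 and clinic visits at Weeks 12 and 24.

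**Analysis.** SAP 12.5: "Descriptive tables displaying the distribution of answers to the items in HCRU at each visit will be provided by treatment group". HCRU appears in none of that section's lists of endpoints analysed by MMRM, logistic regression or CMH test.

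**The concern.** The recall period equals the interval between reports, so a per-patient count over 12 or 24 weeks is available by design. By-visit tables cannot supply it, because the same patient may appear as a user in several tables. They also give no effect size and no interval.

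The treatment of HCRU differs from the rest of the plan in two ways. SAP 12.1 says that endpoints outside the testing strategy are shown with nominal p-values and 95% CIs, and HCRU gets neither. MSQ, EQ-5D VAS and WPAI, which sit under the same objective, each get a modelled comparison in SAP 12.5.

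At stake is whether a randomised secondary endpoint ends with a treatment estimate. There is also a mismatch to tidy: the current protocol still describes a change from baseline that the SAP has dropped.

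**Working it through.** **Plan's own figure.** The documents contain no sizing figure or event rate for HCRU. Their only power figures, about 94% and 99%, concern the primary endpoint. They reproduce (94.3-94.6% and 99.7-99.8%) but have no bearing here. The only input taken from them is 280 patients per arm (Protocol 16.10).

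**Coverage by schedule, with a 4-week recall**

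| Reports used | Weeks covered |
|---|---|
| Week 12 only | 4 (Weeks 9-12) |
| Week 24 only | 4 (Weeks 21-24) |
| Both named endpoints | 8 of 24 |
| Weeks 4, 8, 12 | 12 of 12 |
| Weeks 4 to 24, all six | 24 of 24 |

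**Gain from summing k reports.** Let λ be the event rate per patient per 4 weeks and φ the between-patient overdispersion, both assumed, with n per arm. Then SE(log rate ratio) = √[(2/(kλ) + 2φ)/n]. The ratio to a single report does not depend on n:

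ratio = √[(1/(kλ) + φ)/(1/λ + φ)]

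For k = 3:

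| λ | φ | Calculation | Ratio | SE cut |
|---|---|---|---|---|
| any | 0 | √(1/3) | 0.577 | 42% |
| 0.05 | 1 | √(7.667/21) | 0.604 | 40% |
| 0.1 | 3 | √(6.333/13) | 0.698 | 30% |
| 0.3 | 3 | √(4.111/6.333) | 0.806 | 19% |

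The 42% is therefore a ceiling. Rare items come near it; commoner and more variable items, as routine visits may be, fall well short.

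**Interval width, Poisson, 280 per arm.** Events per arm = 280 × λ × k. The 95% CI factor is exp(1.96 × √(2/events)).

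| Assumed λ | One report: events, factor | Three reports: events, factor |
|---|---|---|
| 0.01 | 2.8, ×/÷ 5.2 | 8.4, ×/÷ 2.6 |
| 0.02 | 5.6, ×/÷ 3.2 | 16.8, ×/÷ 2.0 |
| 0.05 | 14, ×/÷ 2.1 | 42, ×/÷ 1.5 |

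At λ = 0.02 the unrounded factor for three reports is 1.97. A rate ratio would have to be below 1/1.97 = 0.51 before the interval excluded 1.

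**The case against.** The descriptive approach is deliberate and disclosed in SAP Section 18. HCRU lies outside the testing strategy, and its objective is well served by HIT-6, MSQ, EQ-5D VAS and WPAI. Describing low counts rather than modelling them is defensible. This stands, and it keeps the severity low. It does not explain why HCRU is exempt from the general rule in SAP 12.1.

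The names of the two endpoints might lead a reader to infer that the Week 4, 8, 16 and 20 reports are discarded. The documents do not support that: SAP 12.5 tabulates every visit by arm. Only the summation and the contrast are missing.

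The response format is not shown. SAP 19.1.7 speaks of numbers of visits and stays, while Section 18 speaks of response categories. If answers are banded they cannot be summed, so the remedy must allow for that.

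Coverage is complete only by schedule. Protocol Panel 2 allows completion up to 3 days early and visit shifts of 2 days, so recall windows can leave gaps or overlap. SAP 19.2.1 maps Withdrawal Visit answers to Visit 5 or Visit 8. Counting rules are needed, but these points do not undo the case.

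Protocol 16.8.7 has a general rule that continuous scales follow the HIT-6 model. It does not name HCRU, and the specific text in SAP 12.5 gives tables only.

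**Conclusion.** The point holds as a gap in analysis. HCRU is collected so that 12-week use per patient could be derived and compared between arms, and the plan does neither.

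The size of the gain depends on rates that the documents do not give. For a 12-week sum it is at most a 42% cut in the standard error, and about 19% at an assumed rate of 0.3 with overdispersion 3. At an assumed 2 events per 100 patients per 4 weeks, the Poisson interval narrows from ×/÷ 3.2 to ×/÷ 2.0 per 12-week period.

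A reader might go further and infer that the present plan would hide a real fall in emergency or hospital use which the summed analysis would reveal. That is not supported. Sparseness is itself an assumption, and at the rate just used the summed analysis would still exclude no effect only for roughly a halving. The gain is an estimate with an honest interval, not assured detection.

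No primary or key secondary conclusion is affected. This is a low-severity, cheap improvement.

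**What to change.** - **SAP 19.1.7:** for each item, derive the number of events over Weeks 1-12 (Week 4, 8 and 12 reports) and Weeks 13-24 (Week 16, 20 and 24 reports). State how Withdrawal Visit answers mapped to Visit 5 or 8 and overlapping recall windows are counted.
- **SAP 12.5:** compare each dose with placebo by negative binomial regression, with the log number of completed reports as offset, adjusted for the baseline 4-week count and the MHD stratum. Report rate ratios with nominal 95% CIs.
- **Fallback:** if events are too few to fit, or answers prove to be banded, report the proportion of patients with any use in the period, with the difference and an exact CI.
- Keep the by-visit tables. Align the HCRU wording in the protocol Synopsis and Panel 3 with the SAP.
- If this is added after unblinding for the placebo-controlled report, label it post hoc.

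**Cost.** No new assessments and no alpha spent. Five items over two periods make 10 models, and two doses make 20 nominal rate ratios outside multiplicity control. Some models may fail to fit, and the results should be presented as descriptive.

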ICD-10	International Statistical Classification of Diseases and Related Health Problems, 10 th Revision		
ICH	International Council for Harmonisation of Technical Requirements for Pharmaceuticals for Human Use		
ICMJE	International Committee of Medical Journal Editors		
IMP	investigational medicinal product		
IND	Investigational New Drug Application		
IRB	institutional review board		
IRR	infusion related reactions		
IRT	interactive response technology		
IV	intravenous		
LDL	low density lipoprotein		
Lu	Lundbeck		
MBS	most bothersome symptom		
MHDs	monthly headache days		
MMDs	monthly migraine days		
MMRM	mixed model for repeated measurements		
МОН	medication overuse headache		
MSQ v2.1	Migraine-Specific Quality of Life Questionnaire Version 2.1		
NA	not applicable		
NAb	neutralizing antibody		
OC	observed case(s)		
PCR	polymerase chain reaction		
PCS	potentially clinically significant		
PGIC	patient global impression of change		
PR	specific ECG interval describing atrioventricular conduction		
PRO	patient-reported outcome		
Q12W	every 12 weeks		
QP	qualified person		
qPCR	quantitative polymerase chain reaction		
QRS	specific ECG interval describing ventricular depolarization		

QT	specific ECG interval describing ventricular depolarization/repolarization	
QT _c	heart-rate corrected QT interval	
QT_{cF}	heart-rate corrected QT interval using Fridericia's correction formula	
RNA	ribonucleic acid	
RR	specific ECG interval describing the ventricular depolarization/repolarization cycle	
SAE	serious adverse event	
SAP	Statistical Analysis Plan	
SAS	statistical software package from the SAS [®] Institute	
SD	standard deviation	
SNP	single-nucleotide polymorphism	
SOC	system organ class	
SUSAR	suspected unexpected serious adverse reaction	
TEAE	treatment-emergent adverse event	
TFL	tables, figures and listings	
TMF	trial master file	
TNC	trigeminal nucleus caudalis	
TSH	thyroid stimulating hormone	
WPAI	Work Productivity and Activity Impairment	

Major Changes Since Last Edition

The following summarizes the major changes since the last edition of this Clinical Study Protocol. The changes are made to align with study-specific documents developed after the finalisation of the protocol, for consistency and alignment across sections, or to reflect the changes to implement for the remainder of the study. Minor wording clarifications/edits are also made but not included in the list below.

General:

Text and panels related to the interim analysis are deleted throughout the protocol as Sponsor decision was taken to cancel the interim analysis and inform sites as per memo *18898A Interim Analysis* (dated 03-Mar-2021).

Text is added throughout the protocol to clarify that only those patients who withdraw prior to Week 24 will undergo Exit Interview. This is done for consistency and alignment across sections.

Text about requirement for eDiary data review is deleted throughout the protocol, as site staff are not required to conduct a review of eDiary data at each study visit.

Chapter/Section Number	Section Title	Change
Synopsis	Study Methodology	Updated : Bullet 5 – to align with the update under 3.1 Overview of the Study Design (bullet 1) – see below.
Synopsis	Target Patient Population	Updated: Inclusion Criteria bullet 4 – to align with the update under 5.3 Selection Criteria (Inclusion Criterion 9) – see below.
Synopsis	Assessment Details	Updated: To align with the update under 9.2.4 Most Bothersome Symptom (MBS) – see below.
Panel 2	Screening and Baseline Procedures and Assessments	Updated: To align with the update under 9.1.1 Demographics and Baseline Characteristics – see below.
Panel 2	Footnotes	 Updated: Footnote a: text related to 'requirement of screening assessments prior to the Baseline Visit' is deleted for clarification purposes. Footnote t: clarifying text related to 'serum testing for pregnancy' is added to align with the Laboratory Services Agreement (version 1.0, dated 31-Mar-2020) effective at study start. Footnote u: to align with the information in section 9.5.1 Exit Interview (subset). Footnote y: to align with the assessments ticked in Panel 2.

In addition, the following changes have been implemented:

Chapter/Section Number	Section Title	Change
Chapter 3	3.1 Overview of the Study Design	 Updated: Country is added as a stratification factor to align with the Randomization Specification (signed 12-Dec-2019) and Endpoint IRT Specification (version 1.0, dated 11-Feb-2020). Both documents were effective at study start. Sponsor is deleted from list of personnel who are without access to information on individual treatment codes during the study. Following the data-base lock for the Placebo-controlled Period, Supresented in which is discussed in the process.
Chanton 2	2.2 Detionals for the	Sponsor personnel involved in the review of the CSR were unblinded to individual treatment codes.
Chapter 3	Study Design	 Added: Clarifying text to explain: the definitions of EM or CM (number of migraine and headache days) according to the eligibility criteria. that patients with concurrent Medication Overuse Headache were allowed to be included in the study as aligned with the eCRF (effective at study start). the capture of aura occurrence and migraine medication for qualifying a migraine day in the eDiary.
Chapter 5	5.3 Selection Criteria	 Updated: Inclusion Criterion 9: clarification is made that the 28-day screening period was calculated relative to the Screening Visit date (and not the randomization date) as aligned with the Project Design Specification (version 1.0, effective at study start). Inclusion Criteria 9 and 10: reference is added to the definitions explained in new section 9.1.3 Classifications for Eligibility – see below. Inclusion Criterion 14: updated to align with the Clinical Trials Facilitation and Coordination Group (CTFG) guidance to loosen the requirements for contraception during study conduct. Update applies after enrolment was completed and after completion of the Placebo-controlled Period. Exclusion Criterion 15: to align with the CTFG guidance to remove the requirements for contraception during study conduct. Update applies after enrolment was completed and after completion for envection for the requirements for contraception during study conduct. Update applies after enrolment was completed and after completion of the placebo-control for the requirements for contraception during study conduct. Update applies after enrolment was completed and after completion for envection of the requirements for contraception during study conduct. Update applies after enrolment was completed and after completion of the Placebo-controlled Period.
Chapter 7	7.2 Use of Coronavirus Disease 2019 Vaccine	Added: New section regarding use of the COVID-19 vaccine as per memo 18898A COVID-19 Vaccine Guidance (dated 26-Mar-2021) which was provided to sites.
Chapter 8	8.1 Overview	Updated: Text related to 'requirement of screening assessments prior to the Baseline Visit' is deleted for clarification purposes. Added: New text to explain that headache data from the eDiary will be made available during the study to site staff for the remainder of the study.
Chapter 8	8.2 Screening Visit (Visit 1)	Added: Clarifying text to align with the main master Informed Consent Form (version 3.0, dated 27-May-2020) to explain that some patients were invited to attend up to two Screening Visits to complete all assessments at screening.

Chapter/Section Number	Section Title	Change
Chapter 8	8.2.3 Re-screening	Added: Text to explain that rescreening was allowed for patients being in quarantine due to a positive COVID-19 test as per memo 18898A COVID-19 Extension of the Screening Visit or Rescreening (dated 05- Nov-2020) which was provided to sites.
Chapter 8	8.8 Unscheduled Visit	Added: Clarifying section to explain when an unscheduled visit can occur and which assessments can be performed, as aligned with the eCRF (effective at study start).
Chapter 9	9.1.1 Demographics and Baseline Characteristics	Updated: Smoking and alcohol consumption is corrected to substance use and moved from Screening to Baseline Visit in Panel 2. This is to reflect the collection of other substance use during the Screening Period as aligned with the eCRF (effective at study start).
Chapter 9	9.1.2 Diagnostic Assessments	Deleted: Definition of a migraine day as a corrected definition is added to new section $9.1.3$ – see below.
Chapter 9	9.1.3 Classifications for Eligibility	Added: New section to explain the definitions of a migraine day, headache day and eDiary compliant day (linked to inclusion criteria 9 and 10) applied when the patients were enrolled in the study. Definitions are aligned with the eligibility algorithm in the Project Design Specification (version 1.0, effective at study start).
Chapter 9	9.1.4 Definitions for Baseline Disease Activity and Analysis	Added: New section to explain the definitions applied for calculation of number of EM/CM patients (and low/high frequency EM patients) for subgroup analyses. Definitions are based on IHS guidelines ⁴² and are aligned with the Statistical Analysis Plan (version 2, dated 13-Oct-2021).
Chapter 9	9.2 Efficacy Assessments	Added: Sentence added about PRO completion for consistency and alignment with other sections (8.5 IMP Visits, 9.3 Pharmacoeconomic Assessments, 9.7 Order of Assessments). Aligned with the Project Design Specification (version 1.0, effective at study start).
Chapter 9	9.2.2 eDiary	Deleted: Text for missed completion of eDiary is deleted as it is not in alignment with the Project Design Specification (version 1.0, effective at study start).
Chapter 9	9.2.3 Patient Global Impression of Change (PGIC)	Updated: Numerical representation of PGIC scoring is corrected to align with the coding of the responses done for similar clinical outcome assessments in other studies and to align with the Statistical Analysis Plan (version 2, dated 13-Oct-2021).
Chapter 9	9.2.4 Most Bothersome Symptom (MBS)	Updated: Text is corrected to indicate that patient will rate improvement in the symptom from baseline (and not screening) to align with Panel 2 and the Project Design Specification (version 1.0, effective at study start). Updated: Text is corrected to include additional symptoms (mental cloudiness, fatigue, pain with activity, mood changes, other) to align with the eCOA specifications in the Project Design Specification (effective at study start).
Chapter 9	Panel 5	Updated: Clarifying text is added to footnotes to align with the Laboratory Services Agreement (version 1.0, dated 31-Mar-2020) effective at study start. This applies to the requirement for reflex testing for TSH, confirmatory testing for serology, microscopic evaluation for urine and serum testing for pregnancy.

Chapter/Section Number	Section Title	Change
Chapter 9	9.6.3 Blood Sampling for Metabolomic and/or Proteomics	Updated: Gene expression profiling is corrected to metabolomic and/or proteomics.
Chapter 10	10.2 Pregnancy	Updated: Text regarding partner pregnancy is removed as there is no longer requirement to collect data on pregnancies for female partners of male study subjects in eptinezumab studies.
Chapter 12	Monitoring Procedure	Deleted: Text regarding collection of medical history for the prior 3 months is removed to align with eCRF (effective at study start). Updated: Clarifying text is added for acceptable documented evidence of previous treatment failures to reflect the requirements when the patients were enrolled in the study. Added: Text to explain that remote source data verification may be conducted by CRA in accordance with local and national regulations if on-site visits are not possible.
Chapter 16	16.9.1 Analysis of Adverse Events	Updated: Clarifying text is added that the TEAE applies during or after administration of IMP.
Appendix II	Vaccinations	Added: COVID-19 vaccine guidance is added as per memo 18898A COVID-19 Vaccine Guidance (dated 26-Mar-2021) which was provided to sites.

1 Introduction

